An ensemble model was developed and named the precise treatment allocation (PTA) model in our study. It could accurately predict the survival probability of each patient by alternating the different treatments. The inputs of the PTA model mainly comprise four modules: (a) liver function, such as serum albumin, serum bilirubin, and coagulative function indexes; (b) tumor burden, including serum alpha-fetoprotein (AFP), tumor size, and tumor number; (c) demographic data, such as age and gender; and (d) routine laboratory indications, such as routine blood examination and kidney function indexes. To further estimate the predictive performance of the PTA model, it was compared with other prognostic models, including widespread clinical guidelines (BCLC, BCLC B sub-classification ^[9], HKLC, and the most recent Italian Liver Cancer [ITA.LI.CA] staging system ^[10]), other tumor-burden-based models (up-to-seven model ^[11], four-and-seven model ^[12], and six-and-twelve model ^[13]), and models incorporating other parameters (hepatoma arterialembolization prognostic [HAP] score, modified HAP [mHAP] II score ^[13], mHAP III score ^[14], albumin-bilirubin [ALBI] score ^[15], and the model to estimate survival in ambulatory HCC patients [MESIAH] ^[16]), by estimating the auROC and C-index.

Here, HCC patients could achieve two potential survival rates and predicted median survival times (MSTs) by choosing TACE or LR. The ideal LR candidate is defined as a patient whose MST could be extended by more than 50% compared with the MST of primary treatment if LR is adopted in the model. Similarly, ideal TACE candidates are those with an additional survival benefit of more than 50% compared to LR allocation in TACE prediction time. Considering that BCLC and HKLC ^[17] have clearly defined LR and TACE candidates, the ideal LR and TACE candidates of the PTA model were compared with candidates recommended by these two widely used guidelines.

5. Web implementation

After train and validation, the optimized PTA model was implemented as a web

interface, which generates the MST and depict integrated survival curves composed of LR and TACE according to the clinic parameters of specific patients provided by users. Relative algorithms of web development were described in the supplement 1.

6. Statistical analyses

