Continuous and normally distributed variables were expressed as mean with a standard difference (SD) and compared using Student's t-test, while non-normally distributed variables were presented as median with interquartile range (IQR) and compared using the non-parametric Mann–Whitney U test. Categorical variables were expressed as numbers and percentages and tested by Fisher's exact test or the χ^2 test.

Overall survival (OS) was defined as the time interval between initial TACE or LR and all-cause death. Patients who survived up to the last follow-up date (October 15th, 2021) or were lost to follow-up were censored. Survival curves were displayed using the Kaplan–Meier (K-M) method and compared with the log-rank test.

Python software was applied for train AI models and detailed codes were uploaded as supplements (<https://github.com/ApocalypseZ/Survival>). R software and related packages (survival, rms, reportROC, survminer, and ggplot2) were adopted to conduct statistical analysis and plot figures. $P < 0.05$ was considered statistically significant.

Results information for studies

Basic clinical characteristics

In this multicenter study, 4991 patients met the selection criteria and were included. Of these, 1916 patients (38.39%) were amenable to LR while 3075 patients (61.61%) submitted to TACE (Figure 1). 4192 (84%) and 799 (16%) patients were divided into train and validation sets, respectively. Among train set, 1622 (38.7%) were underwent LR while 2570 (61.3%) adopted TACE treatment. In validation set, 294 (36.8%) and 505 (63.2%) were allocated to LR and TACE treatment, respectively. The demographic and clinicopathological characteristics of the cohort are shown in Table 1. The variables associated to tumor burden were lower in the LR group than those of the TACE group in overall cohort: (a) The largest tumor diameters were smaller in the

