the LR and TACE candidates were determined following the BCLC and HKCL guidelines. Among the patients who underwent LR therapy (Supplement 6A-C), the PTA model identified 1386 potential LR candidates, BCLC guidelines selected 1196 cases, and HKCL chose 1765 candidate patients. K-M cures clearly showed that the survival difference between recommended and non-recommended populations was the largest in the PTA model compared with other guidelines. Meanwhile, the hazard ratio (HR) calculated by Cox regression analysis was 10.6, 2.02, and 1.93 respectively in the PTA model, BCLC, and HKCL guidelines (non-recommended as reference). Likewise, among the patients who accepted TACE, the PTA model, BCLC, and HKCL guidelines discriminated 323, 964, and 521 cases, respectively. The HR for the PTA model, BCLC, and HKCL guidelines was 25.4, 0.901, and 0.503, respectively (Supplement 6D-F).

Moreover, the LR candidates recommended by the PTA model had a prolonged OS compared to those suggested by BCLC and HKLC (Figure 2A); a similar conclusion was reached for the TACE group (Figure 2B). Intriguingly, the PTA model also found potential allocation “error” populations in the TACE and LR groups, depicted as hypothetical K-M curves (Figure 3A-B). The MST predicted by the PTA model was significantly higher compared with that of the original therapy allocation, suggesting that alternative therapies can enable patients to achieve a better prognosis and that mistaken allocation either to LR or TACE is still abundant. The patients with actual treatment and LR or TACE candidates are clearly shown in Figure 3C. Regarding the original LR allocation, 1458 cases had the right allocation, while 458 “model-found” cases were misled and should have been given TACE therapy. Similarly, there were abundant erroneous allocations among the original TACE allocations (2752, 89.5%).

Given that BCLC, the HKLC staging system, and PS could affect the prognosis of the potential benefit-gained population, we stratified patients into different BCLC subgroups (BCLC 0-A, BCLC B, and BCLC C stages; Supplement 7), HKLC subgroups (HKLC I-II and HKLC III; Supplement 8), and different PS (PS0 and PS1; Supplement 9). The PTA model could accurately select benefit-gained patients for LR

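### The Figure 3A-B curve for the treatment not received is model output, not overall survival as the plan defines it, so its Kaplan–Meier label and the claim of significance have no observed deaths behind them

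*Combined protocol and SAP*

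**What the plan says.** Section 6 (Statistical analyses) fixes the endpoint: "Overall survival (OS) was defined as the time interval between initial TACE or LR and all-cause death". It fixes the censoring rule: "Patients who survived up to the last follow-up date (October 15th, 2021) or were lost to follow-up were censored". It also names the method for survival curves: "Survival curves were displayed using the Kaplan–Meier (K-M) method and compared with the log-rank test". The threshold is P < 0.05.

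Section 4 (Model estimation) describes what the model produces: "HCC patients could achieve two potential survival rates and predicted median survival times (MSTs) by choosing TACE or LR". Section 5 and the Results on web development add that it returns a survival curve, month by month, under each treatment.

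The Results (Comparison with clinical guidelines) then state that "the PTA model also found potential allocation “error” populations in the TACE and LR groups, depicted as hypothetical K-M curves (Figure 3A-B", and that "The MST predicted by the PTA model was significantly higher compared with that of the original therapy allocation". From this they infer that switching treatment can improve prognosis and that misallocation is common: 458 LR patients and 2752 TACE patients (89.5%).

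**The concern.** Each patient in this dataset is analysed under one treatment, LR or TACE. Survival under the other was not observed, so one side of the Figure 3A-B contrast cannot meet the Section 6 definition of OS. A Kaplan–Meier curve summarises observed event and censoring times, and a test of significance assumes that the compared values are outcomes with sampling variation. Predictions are neither.

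At stake is the displayed support for calling 3210 patients (458 + 2752) misallocated and for saying that they would do better on the other treatment. The same model runs the public web tool. The defect does not depend on how the flagged patients were selected; it would be there in an unselected group too.

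**Working it through.** **1. The plan's own counts reproduce.** 1458 + 458 = 1916 (LR). 3075 − 323 = 2752 (TACE), and 2752/3075 = 89.5%.

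**2. Definition against use.** Section 6 needs a date of death or a censoring date. For the treatment not received neither exists, so the curve rests on the two predicted survival rates or the two predicted MSTs of Section 4. At least three constructions are possible: predicted medians used as event times, averaged individual predicted curves, or times simulated from the model. The text available names none of them, and it names no test behind *significantly*. Section 6 lists the log-rank test for curves and the t-test or Mann–Whitney test for continuous variables. In any of them the predicted values would enter as if they were independent observed outcomes, and the error in the fitted model would not enter at all.

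**3. If predicted medians were the event times.** A predicted median below 12 months is the same as a predicted 1-year death risk above 50%. The curve would therefore show, as dead by 12 months, only the share of patients with risk above 50%.

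Inputs: 1-year survival of 91.7% (LR) and 74.8% (TACE), so mortality of 8.3% and 25.2%; 1-year AUC of 0.873 (0.805–0.941) for LR and 0.893 (0.858–0.928) for TACE.

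Model (an assumption): calibrated predictions with logit(risk) = μ + σz, z standard normal. μ is solved so that mean risk equals the stated mortality, and σ so that the AUC equals the stated AUC. Then the share with median below 12 months = Φ(μ/σ), and the fraction lost = 1 − share/mortality.

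- LR: μ = −3.55, σ = 1.86, share = Φ(−1.91) = 2.8%. Lost: 1 − 2.8/8.3 = 66%. Over the AUC interval: 88% to 36%.
- TACE: μ = −1.95, σ = 2.35, share = Φ(−0.83) = 20.3%. Lost: 1 − 20.3/25.2 = 19%. Over the AUC interval: 28% to 12%.

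More than half is lost only if the 1-year AUC is below about 0.91 (LR) or 0.78 (TACE).

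**4. What a log-rank test would then do.** This was simulated with no treatment difference and calibrated predictions. Weibull proportional-hazards survival was fitted to stated or derived 1-, 3- and 5-year survival, with a normal log-risk of SD 0.6 to 1.5. Censoring was set from the stated follow-up quartiles (an assumption), with 300 runs per setting. Predicted medians, all counted as deaths, were tested against observed OS.

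- TACE, n = 2752, whole-arm survival: mean z of +4.5, +0.7, −0.7 and −1.4 across SD 0.6, 0.9, 1.2 and 1.5, with rejection of 100%, 6%, 5% and 21%. Positive z is against the hypothetical curve, so the direction changes with discrimination.
- LR, n = 458, whole-arm survival (91.7/79.6/70.8%): rejection favours the hypothetical curve in about 88–100% of runs.
- LR, n = 458, survival implied by the stated hazard ratio of 10.6: solve w·x + (1 − w)·x^10.6 = S with w = 1458/1916 = 0.761. At 1 year x = 0.972 and x^10.6 = 0.741; check: 0.761 × 0.972 + 0.239 × 0.741 = 0.917. At 3 and 5 years the same equation gives about 41% and 21%. With 74/41/21%, favourable rejection is about 0% and unfavourable rejection 0–94%. The other split that the Results allow (1386 recommended, 530 not) gives about 76/45/26%.

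A log-rank test on such curves is therefore miscalibrated, but with no fixed direction.

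**5. If averaged predicted curves were plotted.** Averaging calibrated individual survival functions keeps deaths before each patient's median, so steps 3 and 4 do not apply. Step 2 still does.

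**The case against.** The documents are open about the status of these curves: they are called hypothetical and the MST is called predicted. No P value is printed for Figure 3, no test is named, and the figure and Supplement 1 are not available here. Averaged predicted curves fit the text as well as predicted medians do, since the model gives monthly survival under each treatment. In that case the curves are mislabelled rather than wrong in shape. All of this stands, and it makes steps 3 and 4 conditional.

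Two stronger readings are tempting, and the documents support neither. A reader might infer that most early deaths are erased. On the stated AUCs that is so at 12 months for LR at the point estimate, but not for TACE, and only under the predicted-median construction. A reader might also infer that a log-rank test would almost always favour the alternative falsely for the 458 LR patients. That needs them to have the survival of the whole LR arm, which conflicts with the reported hazard ratio of 10.6 between recommended and non-recommended LR patients, taken here as worse survival in the non-recommended (the stated reference direction is unclear). With the implied survival, the favourable excess disappears.

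The objection does not rescue the inference. Calling a curve hypothetical does not give it observed events, and *significantly* claims a statistical comparison that the data cannot supply.

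**Conclusion.** The point holds in two parts. Unconditionally, the curve for the treatment not received is not OS as Section 6 defines it. The Kaplan–Meier label and the claim of a significantly higher predicted MST are unsupported by observed events, whichever construction and test were used. Conditionally, if predicted medians were the event times, the curve is a distribution of medians across patients. It then loses about 66% (36–88%) of 1-year deaths for LR and about 19% (12–28%) for TACE, and any log-rank result is miscalibrated in a direction that depends on the group's survival and on model discrimination.

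The sizes assume calibrated predictions, logit-normal risk, and whole-arm mortality and AUCs that carry over to the flagged patients. The documents do not show that the curves were in fact built from medians or that a log-rank test was run on them.

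**What to change.** - State how the Figure 3A-B curves were built and what lies behind *significantly*.
- For the same patients, plot the average of the individual PTA-predicted survival functions under LR and under TACE, labelled 'model-predicted survival'.
- Overlay the observed Kaplan–Meier curve (Section 6 OS) only against the prediction for the treatment actually received, where it serves as a calibration check.
- Report differences in averaged predicted survival at 1, 3 and 5 years with a bootstrap interval that refits the model.
- Mark any part of a curve beyond the follow-up as extrapolation. The web example gives an LR MST of 78 months, against an upper follow-up quartile of 69.2 months for LR. A hard cut at 60 months would hide such medians, so marking is preferable.
- Apply no log-rank test and no *significantly* to curves built from predictions, and reword the conclusion as a model prediction.

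Cost: no new data or patients, since the monthly predictions already exist. The bootstrap takes computing time because the ensemble has six component models tuned by cross-validated grid search; hyperparameters may be held fixed to limit this. The displayed gain loses its P value.

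### Predicted median survival both picks out the allocation-error patients and serves as the evidence that they would do better on the other treatment, so it cannot show that misallocation is abundant

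*Combined protocol and SAP*

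**What the plan says.** Section 4 gives each patient two model outputs: "HCC patients could achieve two potential survival rates and predicted median survival times (MSTs) by choosing TACE or LR". An ideal LR candidate is "a patient whose MST could be extended by more than 50% compared with the MST of primary treatment", once the treatment input is set to LR. For TACE, "ideal TACE candidates are those with an additional survival benefit of more than 50% compared to LR allocation in TACE prediction time".

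The Results section on comparison with clinical guidelines describes allocation-error populations in both treatment groups, "depicted as hypothetical K-M curves (Figure 3A-B"). It states that "The MST predicted by the PTA model was significantly higher compared with that of the original therapy allocation". From this it infers that switching treatment could improve prognosis, and it describes the wider picture in these words: "mistaken allocation either to LR or TACE is still abundant". It then counts 1458 LR patients as rightly allocated and 458 as patients who ought to have had TACE, and counts 2752 TACE allocations (89.5%) as errors.

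The text does not define the error populations separately. It names no test and gives no MST, interval or P value for this comparison. It does not say whether the MST of the original allocation is predicted or observed.

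**The concern.** The quantity that identifies the patients is also the quantity offered as proof that they were misallocated. The curve for the other treatment is model output. None of these patients contributes an observed outcome under the treatment not received, so the data could not have contradicted the statement.

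The stakes are considerable. The sentence supports the conclusion that 458 + 2752 = 3210 of 4991 patients (64.3%) had the wrong treatment. The same switched-treatment contrast is given to users of a public website as individual MSTs for LR and TACE.

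**Working it through.** **Inputs.** LR 1916, TACE 3075, training set 4192 of 4991 (Basic clinical characteristics). PTA-selected patients: 1386 among LR-treated, 323 among TACE-treated; 1458 right and 458 wrong in LR; 2752 wrong in TACE (Comparison with clinical guidelines). Threshold: predicted MST ratio above 1.5 (section 4).

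**1. Reproduce the counts.**
- TACE: 3075 − 323 = 2752, and 2752/3075 = 89.5%. Both match. The TACE errors are therefore the complement of the ideal TACE candidates, not a group shown to gain more than 50% from LR.
- LR: 1916 − 1458 = 458, which matches. But 1916 − 1386 = 530, so the right-allocation count and the PTA-selected count differ by 1458 − 1386 = 72, with no explanation.

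**2. Patients flagged by a predicted gain above 50%.** If both MSTs are predicted, every flagged patient has a ratio above 1.5 and all differences have the same sign. For illustration, a two-sided sign test on 458 such patients gives p = 2^(1−458), about 10^−138, whatever the truth.

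Suppose that switching benefits nobody and the predicted log MST ratio is normal noise with mean 0 and SD s. The documents give no uncertainty for predicted MST, so s is an assumption. The share flagged is p = P(Z > ln 1.5 / s), with ln 1.5 = 0.405. The median predicted ratio among those flagged is exp(s × z), where z is the 1 − p/2 normal quantile.

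| Assumed s | Flagged | Median predicted ratio | True ratio |
|---|---|---|---|
| 0.3 | 9% | 1.67 | 1.0 |
| 0.5 | 21% | 1.87 | 1.0 |
| 0.7 | 28% | 2.13 | 1.0 |

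This table illustrates the above-50% switch group only.

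**3. The complement group, which the TACE count is.** A TACE patient is counted as an error unless predicted TACE MST exceeds 1.5 times predicted LR MST. If a model predicts equal survival under both treatments, nobody reaches 1.5 and 100% are labelled misallocated. The group can also contain patients with a predicted TACE advantage of up to 50%.

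Under the same null, the share flagged is Φ(ln 1.5 / s), and the geometric mean predicted ratio in the flagged is exp(s × φ(ln 1.5 / s) / Φ(ln 1.5 / s)). At s = 0.3 this gives 91% flagged and a ratio of 1.05. In 200 simulated null trials per setting, a paired signed-rank test favoured the other treatment in 100% of runs at s = 0.3 or more, but in only 2% to 3% at s = 0.1.

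Now let the log LR/TACE ratio be normal with its mean set so that 89.5% are flagged:

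| Assumed s | Geometric mean LR/TACE in the flagged | Flagged with a predicted LR gain above 50% |
|---|---|---|
| 0.2 | 0.89 | 0% |
| 0.278 | 1.00 | 5% |
| 0.4 | 1.19 | 25% |
| 0.6 | 1.60 | 51% |

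So 2752 does not reveal how many TACE patients have a predicted LR gain above 50%.

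**4. Do other results test the switched prediction?** The AUCs, C-index and calibration compare predictions with observed survival, which is survival under the treatment received. The hazard ratios of 10.6 (LR) and 25.4 (TACE) use observed survival, so they are not circular in this way. But they compare recommended with non-recommended patients on the same treatment, which shows prognosis and not the effect of switching. The counts cover all 4991 patients, of whom 4192 (84%) trained the model.

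**The case against.** The strongest reply is that the text is hedged: the curves are called hypothetical, the populations potential, and the conclusion only suggested. That is fair for this sentence. The hedging stops in the same paragraph, where 458 and 2752 patients are described as wrongly allocated without qualification.

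A second reply is that the circularity is not complete, and this stands. A reader might infer that the result is true by construction for everyone flagged, or that any model, even pure noise, would produce it. The documents do not support that. The TACE errors are a complement group and make up 2752 of 3210 flagged patients (86%). For them a longer predicted MST is favoured but not assured, and the null at s = 0.1 shows a case where it does not appear.

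Nor can the first simulation table be read as the size of the reported effect. A null centred on zero flags the same share in both arms, whereas the documents report 458/1916 = 23.9% in LR and 89.5% in TACE. Noise alone does not explain that asymmetry.

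Finally, a reader might conclude that the P value itself is invalid because predicted curves carry no event uncertainty. Figure 3 is not shown, no test is named, and the comparator may be observed survival, which does carry such uncertainty. That argument cannot be settled from the text.

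**Conclusion.** The inference is unsupported as written. A longer predicted MST in patients identified through predicted MST, with no outcome observed under the other treatment, is not evidence that switching helps or that misallocation is abundant.

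For patients flagged by a predicted gain above 50%, the result is guaranteed, provided that the comparator is also a predicted MST. For the 2752 TACE patients, selection pushes in that direction without guaranteeing it, and the 89.5% depends heavily on counting everyone with no strong predicted preference as an error. If the comparator is observed survival, the guarantee is not exact, but the conclusion still lacks any observed outcome under the other treatment.

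This does not show that PTA's recommendations are wrong, only that this comparison cannot show that they are right. The complement reading rests on the exact match 3075 − 323 = 2752. The simulated figures rest on assumed SDs.

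**What to change.** 1. Drop the significance statement and the conclusion drawn from it. Label Figure 3A-B as model projections in patients selected on model output.
2. Define the error group by one rule, a predicted gain above 50% under the other treatment. Report patients with no clear predicted preference separately. Recount 458 and 2752 on that rule, and reconcile 1386 with 1458.
3. Withdraw the wording that patients ought to have received the other treatment or were allocated in error.
4. If benefit of reallocation is to be claimed, compare observed OS between patients treated in line with the recommendation and those treated against it. Use out-of-fold or validation-set predictions, adjust for the baseline inputs, and give confidence intervals.

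Steps 1 to 3 cost rewording and a recount. Step 4 uses existing data but loses precision. The validation set has 799 patients. If the reported counts scale by 799/4991 = 0.16 (an assumption), the TACE-preferred group there is about 323 × 0.16 = 52 TACE-treated and 458 × 0.16 = 73 LR-treated patients, and the recount may change both. Residual confounding would remain. The validation set is also not fully independent, because its C-index was used in judging PTA the best model. The sponsor should expect a less favourable and less precise result.

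### The 2752 (89.5%) erroneous TACE allocations are all TACE patients who are not PTA TACE candidates; under the document's own 50% rule this is only an upper bound

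*Combined protocol and SAP*

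**What the plan says.** Section 4 (Model estimation) gives each patient two predictions: "HCC patients could achieve two potential survival rates and predicted median survival times (MSTs) by choosing TACE or LR". An ideal LR candidate is a patient "whose MST could be extended by more than 50% compared with the MST of primary treatment if LR is adopted in the model". For the other treatment, "ideal TACE candidates are those with an additional survival benefit of more than 50% compared to LR allocation in TACE prediction time".

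The results on basic clinical characteristics give the group sizes: "1916 patients (38.39%) were amenable to LR while 3075 patients (61.61%) submitted to TACE".

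The results on comparison with clinical guidelines say that, among TACE patients, "the PTA model, BCLC, and HKCL guidelines discriminated 323, 964, and 521 cases, respectively". Among LR patients the PTA model is credited with 1386 LR candidates. A little later, 1458 LR patients are called correctly allocated and 458 are said to have needed TACE. The TACE counterpart follows: "Similarly, there were abundant erroneous allocations among the original TACE allocations (2752, 89.5" (per cent). The same section concludes that "mistaken allocation either to LR or TACE is still abundant", and refers the reader to a figure: "The patients with actual treatment and LR or TACE candidates are clearly shown in Figure 3C".

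**The concern.** The two candidate definitions each require a gain of more than 50%. They cannot both be met, but both can be failed. A patient whose predicted MSTs are close, or who is predicted to live 40% longer on TACE, is neither an ideal LR candidate nor an ideal TACE candidate. If such a patient received TACE, the reported count treats that as an error, although the model's rule does not favour LR.

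The 2752 is the larger of the two counts behind the statement that misallocation is common. As labelled, it can include patients for whom the model favours neither treatment or mildly favours the one they received. The LR counts also raise the possibility that such patients are called right in one group and wrong in the other, in which case the two error rates could not be compared.

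**Working it through.** **Inputs.** TACE patients 3075 and LR patients 1916 (basic clinical characteristics). PTA TACE candidates among TACE patients 323; stated TACE errors 2752 (89.5%); PTA LR candidates among LR patients 1386; LR patients called right 1458 and wrong 458 (comparison with clinical guidelines). Threshold: more than 50% longer MST (section 4).

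**1. Reproduce the stated figure.** 3075 − 323 = 2752, and 2752/3075 = 0.895. Count and percentage both match exactly. The document does not state the derivation, but with 323 as the TACE candidates, the 2752 are their complement.

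**2. What the rule implies.** Let r = MST on LR ÷ MST on TACE.
- LR candidate: r > 1.5.
- TACE candidate: 1/r > 1.5, that is r < 0.667.
- Neither: 0.667 ≤ r ≤ 1.5.

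The complement of the TACE candidates is r ≥ 0.667, which joins the LR candidates to the neither class. Hence, among TACE patients, LR candidates = 2752 − (number in the neither class), and 2752 is the maximum.

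**3. How far the count could move.** The text does not give the size of the neither class. Every size below is an assumption.

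| Assumed neither class among TACE patients | Number | LR-favoured count | Rate |
|---|---|---|---|
| Empty | 0 | 2752 | 89.5% |
| 72/1916 = 3.8% (LR-group residual, if those 72 are neutral) | 116 | 2636 | 85.7% |
| 10% | 308 | 2444 | 79.5% |
| 25% | 769 | 1983 | 64.5% |
| 50% | 1538 | 1214 | 39.5% |

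The rate falls below one half only if at least 1215 TACE patients (1215/3075 = 39.5%) are in the neither class: (2752 − 1215)/3075 = 0.4998.

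**4. The LR group.** 1458 + 458 = 1916, so right and wrong exhaust the group. Had non-candidates been counted as errors, as they are for TACE, the number would be 1916 − 1386 = 530, not 458. The difference is 530 − 458 = 72, which is also 1458 − 1386. If these 72 meet neither threshold, then 1386 + 72 + 458 = 1916, and neutral patients count as right in the LR group but as wrong in the TACE group. The text does not explain the 72.

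**5. The document's own example.** Under web development and clinical application, a patient with predicted MSTs of 15 months (TACE) and 10 months (LR) is said to benefit from TACE. At the printed values the ratio is 15/10 = 1.50, which is not more than 50%; rounding to whole months allows 14.5/10.5 = 1.38 to 15.5/9.5 = 1.63. At face value, such a patient treated with TACE would fall among the errors. The example comes from the concise version of the tool, so it shows only how the rule behaves at the boundary.

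**The case against.** - **The derivation is inferred.** The text never says that 2752 was obtained by subtraction. It could have been counted directly with the LR rule, leaving 323 as the remainder. Then 2752 would be right and the description of the 323 as TACE candidates would be wrong. This cannot be excluded, but it goes against the text's own account of the 323, and one of the two labels would still need correcting.
- **Figure 3C may hold the cross-classification.** The figure is not available here, so its content cannot be called missing. That stands. Whatever the figure shows, the prose calls all 2752 errors and draws its conclusion on that basis.
- **The middle group may be small or empty.** This stands too: no error of a given size has been shown. Even with half of TACE patients in the middle group, 1214 would remain, with 458 in the LR group, so the model's output could still be described as showing many reallocations.
- **Another rule may have been used.** If right meant any predicted advantage for the treatment received, the extra 72 LR patients would be explained. On the TACE side, however, such a rule yields exactly the 323 threshold candidates only if no TACE patient had a mild TACE advantage, which the text does not show. The 72 may also be a typing error.
- **A recount does not make this a true misallocation rate.** Correct. It would still rest on model predictions of the treatment not received, from non-randomised groups that the document says differed significantly. The upper bound applies only to the count under the model's own rule.

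**Conclusion.** The concern holds. The division is correct, but the label is not supported: 2752 (89.5%) is the most that the document's rule allows for TACE patients favoured for LR. Taking the 323 as TACE candidates in the sense of section 4, the text supports only a range from 0 to 2752. How far the true count lies below 2752 depends on the number of TACE patients in the neither class, which the text does not report; the figure is unchanged if that number is zero.

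The LR figure of 458/1916 = 23.9% is not challenged here, but the gap between 1386 and 1458 leaves open whether both groups were judged by the same rule. That the 72 are neutral patients is a possibility, not a finding.

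A smaller fault lies in the LR definition. Its comparison with the MST of the primary treatment, read literally, sets LR against LR for a patient who received LR. The sentence before it introduces one MST for each treatment, so the intended contrast is clear and this is a matter of wording.

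**What to change.** 1. Apply the document's own 50% threshold symmetrically to the two predicted MSTs, as an analytic classification and not a treatment rule: LR-favoured, TACE-favoured, neither.
2. Report the count in each class by treatment received. If Figure 3C already shows this, bring the numbers into the text.
3. Count as misallocated by the model only patients for whom the treatment not received is favoured. Restate the 2752 (89.5%), and the conclusion about how common misallocation is, to match.
4. State how 1386 relates to 1458 and which rule gave 458.
5. In the LR definition, name the alternative treatment as the comparator.

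The cost is a recount from existing predictions and some rewording, with no new data. The stated percentage may fall, or stay at 89.5% if the middle class is empty.
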